### **Tumor Lysis Syndrome (TLS)**

Tumor lysis syndrome (TLS), including fatal cases, has been reported in patients receiving obinutuzumab. During the initial days of obinutuzumab treatment, monitor the laboratory parameters of patients considered at risk for TLS. For treatment of TLS, correct electrolyte abnormalities, monitor renal function and fluid balance, and administer supportive care, including dialysis as indicated. Refer to *paragraph 13.5*.

### **Infections**

Fatal and serious bacterial, fungal, and new or reactivated viral infections can occur during and following obinutuzumab therapy. Patients with a history of recurring or chronic infections may be at increased risk of infection.

A “black-box” warning for obinutuzumab states that reactivation of hepatitis B as well as other serious viral infections (e.g., infections caused by cytomegalovirus, Varicella zoster virus, herpes simplex virus, JC virus, and HCV) that were new, reactivated, or exacerbated have been reported with the B cell-depleting antibody rituximab mainly in patients who had received the drug in combination with chemotherapy or as part of a hematopoietic SCT. The risk of such infections with obinutuzumab is unknown.

### **Thrombocytopenia**

Monitor all patients frequently for thrombocytopenia and hemorrhagic events, especially during the first cycle. In patients with Grade 3 or 4 thrombocytopenia, monitor platelet counts more frequently until resolution and consider subsequent dose delays of obinutuzumab. Transfusion of blood products (i.e., platelet transfusion) may be necessary. Consider withholding concomitant medications, which may increase bleeding risk (platelet inhibitors, anticoagulants), especially during the first cycle.

In the event of severe thrombocytopenia (platelet count < 10,000/ $\mu$ L) and/or symptomatic bleeding (irrespective of platelet count) in patients who are not receiving concomitant anticoagulants or platelet inhibitors: Hold obinutuzumab until thrombocytopenia or symptomatic bleeding resolves. If Cycle 1 Day 8 is delayed, then skip Day 8 and administer Day 15 as previously scheduled (if thrombocytopenia or symptomatic bleeding has resolved). If Cycle 1 Day 15 is delayed, then skip Day 15 dosing and administer Cycle 2 Day 1 of obinutuzumab as scheduled (if thrombocytopenia or symptomatic bleeding has resolved).

In the event of thrombocytopenia with platelet count < 20,000/ $\mu$ L and/or symptomatic bleeding (irrespective of platelet count) in patients who are receiving concomitant anticoagulants or platelet inhibitors:

- Hold obinutuzumab until thrombocytopenia or symptomatic bleeding resolves. If Cycle 1 Day 8 is delayed, then skip Day 8 and administer Day 15 as previously scheduled (if thrombocytopenia or symptomatic bleeding has resolved). If Cycle 1 Day 15 is delayed, then skip Day 15 dosing and administer Cycle 2 Day 1 of obinutuzumab as scheduled (if thrombocytopenia or symptomatic bleeding has resolved).
- For patients who are on LMWH or NOACs, when platelet count < 20,000/ $\mu$ L develops, reduce the dose of LMWH or NOACs used.
- For patients who are on platelet inhibitors when thrombocytopenia with platelet count < 20,000/ $\mu$ L develops, consideration should be given to temporarily pausing the use of platelet inhibitors.

### **Neutropenia**

Severe and life-threatening neutropenia, including febrile neutropenia, has been reported during treatment with obinutuzumab. Monitor patients with Grade 3 to 4 neutropenia frequently with regular laboratory tests until resolution. Anticipate, evaluate, and treat any symptoms or signs of

developing infection. Consider administration of granulocyte colony-stimulating factors (GCSF) in patients with Grade 3 or 4 neutropenia.

Consider dose delays in the case of Grade 3 or 4 neutropenia. Patients with severe and long lasting (> 1 week) neutropenia are strongly recommended to receive antimicrobial prophylaxis until resolution of neutropenia to Grade 1 or 2. Consider antiviral and antifungal prophylaxis.

In the event of febrile neutropenia or neutropenia with infection, hold obinutuzumab until febrile neutropenia or neutropenia with infection resolves.

- If Cycle 1 Day 8 is delayed long enough that the patient is approaching Day 15, then skip Day 8 and administer Day 15 as previously scheduled (if infection or fever has resolved)
- If Cycle 1 Day 15 is delayed long enough that the patient approaching Cycle 2, then skip Day 15 dosing and administer Cycle 2 Day 1 as scheduled (if infection or fever has resolved).

Neutropenia can also be of late onset (occurring more than 28 days after completion of treatment) and/or prolonged (lasting longer than 28 days).

For more details please refer to *Appendix F* or drug IB.

## **14. REMOVAL OF SUBJECTS FROM TREATMENT AND/OR STUDY**

### **14.1. Discontinuation from study treatment**

A patient should discontinue treatment if any of the following occurs:

- completed treatment as per protocol
- unacceptable toxicity that does not allow to give the protocol treatment
- progression, relapse or death at anytime
- refusal of the patient to further cooperate (at any time and for any reasons)
- investigator's decision that the protocol treatment is not anymore in the best interest of the patient

Subject study participation may be ended due to any of the following reasons:

- Initiation of anti-neoplastic therapy in the absence of progression
- Disease progression
- Withdrawal of consent
- Significant subject noncompliance with study drug administration, study procedures, or study requirements
- Investigator's decision to remove the subject from the study, in consultation with the Medical Monitor
- Pregnancy
- The subject is lost to follow-up
- Death

Discontinuation of the study at the request of the Sponsor, a regulatory agency, or an independent ethics committee (IEC).

Patients who discontinue treatment for any cause will continue to be followed for two years for OS. All subjects will be followed until study completion unless consent to do so is specifically withdrawn by the subject.

Study drug may be discontinued in the following instances, in consultation with the Medical Monitor:

- Intercurrent illness that would, in the judgment of the investigator, affect assessments of clinical status to a significant degree. Following resolution of intercurrent illness, the subject may resume study dosing at the discretion of the investigator
- Unacceptable toxicity, or toxicity that, in the judgment of the investigator, compromises the ability to continue study-specific procedures or is considered to not be in the subject's best interest

- Objective evidence based of PD
- Subject request to discontinue for any reason
- Subject noncompliance
- Pregnancy during the study

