#### **14.3. Withdrawal of Consent**

Patients are free to withdraw from the study at any time without prejudice to their treatment. When a patient decides to withdraw from the study, she/he should always be contacted in order to obtain information about the reason for withdrawal and to record any adverse events. When possible, the patient should return for a study visit at the time of, or soon after withdrawal, and the relevant assessments should be performed.

If the patient explicitly states his/her wish not to contribute further data to the study, the assigned FIL Study Coordinator should be informed, and the withdrawal of consent should be documented by the investigator in the patient's case report form. Information from subsequent ambulatory visits, laboratory or instrumental assessments and any other information on the patient status after consent withdrawal won't be collected in the data base or used for analysis. However, both clinical data collected until patient's withdrawal as well as the data coming from the central review will still be considered as available for the study analysis.

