### 15.3. Assessment for restaging

after III\* course and at EOI:

- Measurable lesion assessment on CT scan of neck, chest, abdomen and pelvis, to be performed with and without contrast;
- FDG-PET scan (mandatory);
- Bone marrow biopsy only if positive at baseline.

Patients who achieve a response less than stable disease after first restaging or at EOI are considered out of treatment and will be shifted to survival follow up

\*Within 7 days before cycle IV day 1

**Clinical and Laboratory CMV infections monitoring:** Every two weeks starting from C1D1.

**Prophylaxis for PJP:** all patients will receive PJP prophylaxis during idelalisib treatment and for 2 to 6 months after stopping treatment; patients have to be monitored for respiratory signs and symptoms.

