#### 16.4. Pregnancy

##### Females of Childbearing Potential

Pregnancies and suspected pregnancies (including a positive pregnancy test regardless of age or disease state) of a female subject occurring while the subject is on study drug are considered events to be reported immediately to FIL Pharmacovigilance on the appropriate Pregnancy Form:

e-mail: [[contact]](mailto:[contact])

[contact]

If the subject is on study drug, the study drug is to be discontinued immediately.

The exposure of any pregnant female (e.g. caregiver or pharmacist) to study drug is also an immediately reportable event.

The female should be referred to an obstetrician/gynecologist preferably one experienced in reproductive toxicity for further evaluation and counseling.

The Investigator will follow the female subject until completion of the pregnancy and must notify FIL immediately about the outcome of the pregnancy (either normal or abnormal outcome).

If the outcome of the pregnancy was abnormal (i.e., spontaneous or therapeutic abortion) the Investigator should report the abnormal outcome as a SAE within 24 hours of the Investigator's knowledge of the event through [www.drugvigilance.filinf.it](http://www.drugvigilance.filinf.it).

All neonatal deaths that occur within 30 days of birth should be reported, without regard to causality, as SAEs. In addition, any infant death after 30 days that the Investigator(s) suspects is related to the in-utero exposure to the study drug should also be reported to FIL within 24 hours of the Investigator's knowledge of the event through [www.drugvigilance.filinf.it](http://www.drugvigilance.filinf.it).

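### The last list of Section 14.1 makes stopping study drug discretionary for pregnancy and for progression, in contradiction of Section 16.4 and of the passages that take progressing patients off treatment

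*Combined protocol and SAP*

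**What the plan says.** Section 14.1 of the combined protocol and SAP contains three lists.

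- The opening list is directive: "A patient should discontinue treatment if any of the following occurs". It covers, among other reasons, unacceptable toxicity, progression or relapse, and the patient's refusal to go on. It attaches no Medical Monitor condition. Pregnancy is not on it.
- The middle list gives reasons why study participation may be ended. Pregnancy and progression are on it. Section 14.2 repeats these reasons.
- The last list is permissive: "Study drug may be discontinued in the following instances, in consultation with the Medical Monitor". Its six entries are intercurrent illness, toxicity, progression ("Objective evidence based of PD"), the subject's request, noncompliance and pregnancy ("Pregnancy during the study").

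Other sections deal with the same triggers.

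- Section 16.4, on a pregnancy in a female subject: "If the subject is on study drug, the study drug is to be discontinued immediately".
- Section 15.3: "Patients who achieve a response less than stable disease after first restaging or at EOI are considered out of treatment". The assessments part of the synopsis and Section 10.1 likewise class patients with documented progression as off treatment; 10.1 specifies progression during induction or maintenance.
- Section 13.3 runs maintenance until progression or unacceptable toxicity, with two years as the limit.
- Section 14.3: "Patients are free to withdraw from the study at any time without prejudice to their treatment".

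I found no statement of which passage prevails where they differ.

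**The concern.** A stopping rule should give every site the same instruction for the same event. Here the instruction for a pregnant participant is discretionary and subject to consultation in the section on removal from treatment, and immediate in the pregnancy section. For progression, one list in 14.1 makes stopping discretionary, while another list in the same section and three further passages do not.

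Participant protection comes first, because the two readings on pregnancy differ in both obligation and timing. The event is foreseeable: where applicable, Section 15.2 schedules a pregnancy test before each induction course.

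There is a smaller consequence for the data. Adverse events are collected, and treatment-emergent events defined, up to 30 days after the last dose (Sections 15.9, 16.3 and 17.3). A last-dose date that depends on which text a site follows carries that window with it.

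**Working it through.** The point rests on no sample size, rate or error probability, so there is nothing to compute. The check sets the instructions side by side, trigger by trigger.

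1. **Pregnancy.** Last list of 14.1: *may*, with consultation. Opening list of 14.1: absent. Middle list of 14.1 and Section 14.2: *may*, and about ending participation. Section 16.4: immediate, with no consultation step. Section 14 therefore gives only permissive wording, and the directive text sits in a different section. This is a direct conflict.

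2. **Progression.** Last list of 14.1: *may*, with consultation. Opening list of 14.1: *should*, at any time. Synopsis, 10.1 and 15.3: off or out of treatment. Section 13.3: maintenance ends. None of these opposing passages has a consultation condition. This is a direct conflict, both within 14.1 and with text outside it.

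3. **Unacceptable toxicity.** The last list reads "Unacceptable toxicity, or toxicity that, in the judgment of the investigator, compromises the ability to continue study-specific procedures", under *may*. The opening list puts unacceptable toxicity under *should*, and 13.3 makes it an end point for maintenance. The entry in the last list is also the broader of the two, since it takes in toxicity that interferes with study procedures in the investigator's judgment. This is a lesser inconsistency.

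4. **Patient request.** Last list: *may*, with consultation. Opening list: *should*, on refusal for any reason. Section 14.3 protects the right to leave the study but gives no instruction about stopping drug alone, so it supports the point only indirectly. This is a lesser inconsistency.

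5. **Intercurrent illness and noncompliance.** I found no opposing instruction to stop drug. No conflict.

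The count over the last list is 2 direct conflicts + 2 lesser inconsistencies + 2 without conflict = 6 entries.

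**Data consequence.** The adverse event window closes at last dose + 30 days. If dosing continued for *d* days past the trigger under one reading and stopped at the trigger under the other, the last dose and the end of the window would each fall *d* days apart. The documents give no basis for a value of *d* or for the number of patients affected.

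**The case against.** The strongest reply is that *may* and *should* do not strictly contradict each other. Stopping satisfies both, and no passage tells a site to continue. The last list can be read as the accepted reasons for stopping, handled with the Medical Monitor. Its first entry allows dosing to resume after an illness, so the list also covers temporary interruption, which the opening list does not. The protocol further allows one agent to continue when the other is permanently stopped, so permissive wording about study drug need not clash with the end of protocol treatment. Finally, a site reporting a pregnancy has to use Section 16.4, where the stop instruction stands.

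Much of this holds for toxicity and patient request. There the opposing text is mainly *should*, in the same section, and a site reading 14.1 sees both lists. It is also fair that continued dosing after progression would mean disregarding the opening list and several other passages.

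It does not resolve pregnancy. Even as a list of accepted reasons, discretion after consultation is a different instruction from immediate discontinuation, and Section 14 contains no directive text to correct it. For progression, the number of opposing passages makes the intention easier to guess, but the permissive entry still stands beside them.

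**Conclusion.** The contradiction is real for pregnancy and for progression, and pregnancy is the more serious of the two. Toxicity and patient request are a lesser inconsistency of wording within 14.1. This is a contradictory safety instruction, not merely missing detail. It rests on the text alone and needs no numerical assumption.

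A reader might infer more than the documents support:

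- **That 14.1 makes stopping optional throughout.** It does not. Its opening list is directive for progression, toxicity and refusal; only the last list is permissive.
- **That four of the six entries are mandatory elsewhere.** Only pregnancy and progression meet firm text of that kind. The other two rest mainly on *should*, and 14.3 is about leaving the study.
- **That patients will be kept on drug at some sites.** The wording permits this, but nothing shows that it would happen, and its frequency cannot be derived.
- **That overall survival is distorted.** Section 9.4 measures it from the start of therapy to death, with censoring at last contact. A later stop could change the length of survival follow-up under 10.1, but not the endpoint's definition. The synopsis counts that period from documented progression and 10.1 from treatment discontinuation; this is a separate discrepancy that 14.1 does not cause.
- **That response or serious event reporting is affected.** The last-available-response rule in 9.3 depends on permanent discontinuation of both drugs before cycle 6 is complete, so any effect on response again presupposes continued dosing. Section 16.3 has serious events notified until the last patient's last visit, which is not tied to the last dose.

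What remains on the data side is conditional: if dosing continued under the permissive text, the last-dose date and the 30-day window for adverse events would shift.

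**What to change.** Reconcile the last list of Section 14.1 as follows:

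- on pregnancy, with Section 16.4;
- on progression, with the opening list of 14.1, the synopsis, Section 10.1 and Section 15.3;
- on unacceptable toxicity and patient request, with the opening list of 14.1.

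After the change, each trigger should carry one instruction wherever it appears. If the last list is meant only to cover temporary interruption, or only to record accepted reasons for stopping, it should say so. Which instruction applies to each trigger is for the sponsor to decide; this review does not propose one.

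The cost is wording in one section of the next amendment. Sample size, endpoints and planned analyses do not change.

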#### **14.2. Withdrawal of subjects from the study**

- Circumstances that lead to premature withdrawal of a patient from the trial must be reported by the investigator on the appropriate CRF page.
- Criteria for subject withdrawal include (but are not limited to):
  - death,
  - toxicity
  - violation of inclusion criteria
  - lost to follow up
- Subject study participation may be ended due to any of the following reasons:
  - Initiation of anti-neoplastic therapy in the absence of progression
  - Disease progression
  - Withdrawal of consent
  - Significant subject noncompliance with study drug administration, study procedures, or study requirements
  - Investigator's decision to remove the subject from the study, in consultation with the Medical Monitor
- Pregnancy
- The subject is lost to follow-up
- Death
- Discontinuation of the study at the request of Sponsor, a regulatory agency, or an institutional review board or independent ethics committee (IRB/IEC)

#### **14.3. Withdrawal of Consent**

Patients are free to withdraw from the study at any time without prejudice to their treatment. When a patient decides to withdraw from the study, she/he should always be contacted in order to obtain information about the reason for withdrawal and to record any adverse events. When possible, the patient should return for a study visit at the time of, or soon after withdrawal, and the relevant assessments should be performed.

If the patient explicitly states his/her wish not to contribute further data to the study, the assigned FIL Study Coordinator should be informed, and the withdrawal of consent should be documented by the investigator in the patient's case report form. Information from subsequent ambulatory visits, laboratory or instrumental assessments and any other information on the patient status after consent withdrawal won't be collected in the data base or used for analysis. However, both clinical data collected until patient's withdrawal as well as the data coming from the central review will still be considered as available for the study analysis.

#### **14.4. Patients Lost to Follow up**

Every effort will be made to contact patients who fail to return for scheduled visits. A patient is considered lost to follow-up if no information has been obtained when the last patient has completed the clinical phase of the study. During this time site investigator must document attempts to contact the patient either by phone or letter.

#### **14.5. Premature termination of the study**

The sponsor reserves the right to stop the trial at any time, in accordance with the DSMB. The investigators will be informed of this decision in writing.

The same applies to any investigator willing to discontinue his/her participation to the trial. The investigator must immediately inform the sponsor in writing of this decision.

## 15. STUDY PROCEDURES TIMEPOINTS

### 15.1. Screening period

within 28 days prior to Study Cycle 1 Day 1

All subjects will be screened for study eligibility including:

- Confirmed relapsed/refractory FL\*
  - \* *Histological centralized review is compulsory for start of treatment, but the local pathology report is sufficient for patient enrollment*
- Medical History;
- Physical Examination;
- Height, Weight;
- ECOG;
- Vital Signs;
- B symptoms;
- Hematology including Hemoglobin, Platelets, White blood cell count (WBC) with differential;
- Blood chemistry including creatinine, total bilirubin, LDH, AST, ALT, serum proteins with electrophoresis, immunoglobulin levels;
- Electrocardiogram;
- LVEF by either bi-dimensional echocardiogram or cardiac scintigraphy (MUGA);
- Measurable lesion assessment on CT scan of neck, chest, abdomen and pelvis, to be performed with and without contrast;
- FDG-PET scan (mandatory)
- Pregnancy test (if applicable);
- A bone marrow biopsy with immunohistochemical evaluation;
- Local molecular evaluation of BCL-2 rearrangement on marrow blood;
- Viral tests including HIV, HBsAg, HBsAb, HBcAb, HBV DNA and HCV (HCV RNA required for patient who are HCV antibody positive);
- Monitoring for CMV infection;
- Concomitant medications.

### 15.2. Treatment period (Induction)

Before each course of chemotherapy (within 24 hours prior to Day 1):

- Physical Examination, including weight;
- ECOG;
- Vital Signs;
- B-symptoms;
- Hematology including Hemoglobin, Platelets, White blood cell count (WBC) with differential;
- Blood chemistry including creatinine, total bilirubin, LDH, AST, ALT, serum proteins with electrophoresis, immunoglobulin levels;
- AE assessment;
- Pregnancy test (if applicable);
- Concomitant medications.

At days 8 and 15 during the first cycle:

- Vital Signs;
- Hematology including Hemoglobin, Platelets, White blood cell count (WBC) and neutrophils;
- Blood chemistry including creatinine, total bilirubin, LDH, AST, ALT;
- AE assessment

